1.2. Study Design

This is a Phase 3 randomized, open-label, multicenter study of RDV therapy in participants with severe COVID-19.

Groups

For Part A, approximately 400 participants who met all eligibility criteria and who were not mechanically ventilated were randomized in a 1:1 ratio into one of the following treatment groups:

- **Treatment Group 1:** continued standard of care therapy together with IV RDV 200 mg on Day 1 followed by IV RDV 100 mg on Days 2, 3, 4, and 5
- **Treatment Group 2:** continued standard of care therapy together with IV RDV 200 mg on Day 1 followed by IV RDV 100 mg on Days 2, 3, 4, 5, 6, 7, 8, 9, and 10

Part B will enroll new participants on mechanical ventilation and, after enrollment to Part A is complete, any additional participants. In Part B, up to an additional approximately 5600 participants who meet all of the eligibility criteria will be enrolled, based on whether they are mechanically ventilated at enrollment, to receive:

Mechanically Ventilated Group: continued standard of care therapy together with IV RDV 200 mg on Day 1 followed by IV RDV 100 mg on Days 2, 3, 4, 5, 6, 7, 8, 9, and 10

Extension Group: continued standard of care therapy together with IV RDV 200 mg on Day 1 followed by IV RDV 100 mg on Days 2, 3, 4, 5, 6, 7, 8, 9, and 10

Key Eligibility Criteria

Participants with COVID-19 confirmed by polymerase chain reaction (PCR) who meet the following criteria:

- Willing and able to provide written informed consent (age ≥ 18) or assent (age ≥ 12 to < 18 , where locally and nationally approved) prior to performing study procedures
- Hospitalized
- Oxygen saturation (SpO_2) $\leq 94\%$ on room air or requiring supplemental oxygen at screening
- Radiographic evidence of pulmonary infiltrates

Schedule of Assessments

The date of randomization or enrollment is considered Day 1 and it is expected that all randomized or enrolled participants receive their initial dose of RDV on Day 1.

On Days 1 through 14 or until discharge, whichever is earlier, vital signs including respiratory status will be measured and adverse events (AEs) and concomitant medications will be documented. Laboratory testing will be performed according to standard of care practice with results for white blood cell (WBC) count, hemoglobin and/or hematocrit, platelets, creatinine, creatinine clearance, glucose, total bilirubin alanine aminotransferase (ALT), aspartate aminotransferase (AST), and any SARS-CoV-2 testing being reported to the Sponsor. Clinical status will be recorded on the 7-point ordinal scale for each day.

In addition, even if not performed as standard of care, WBC count, hemoglobin and/or hematocrit, platelets, creatinine, creatinine clearance, glucose, total bilirubin, ALT, AST will be performed at Days 1, 3, 5, 8, 10, and 14 or until discharge, whichever is earlier.

CCI

Randomization

For Part A, participants who met eligibility criteria were randomized in a 1:1 ratio to 1 of 2 treatment groups on Day 1 using an interactive web response system (IWRS) and assigned a subject number. Randomization was not stratified. Part B is not randomized.

Sites

Up to approximately 160 centers globally.

Duration of Treatment

Part A participants received study treatment with RDV for 5 days (Treatment Group 1) or 10 days (Treatment Group 2). In Part B, participants in the Mechanically Ventilated Group and Extension Group will receive RDV for 10 days. If the participant is discharged, RDV treatment will end at that time.

Discontinuation Criteria

Study drug dosing in an individual participant will be placed on hold and may be discontinued, following a review of all available clinical data by the medical monitor and discussion with the investigator, if any of the following occurs:

- Any serious adverse event (SAE) or \geq Grade 3 AE suspected to be related to RDV.
- Any elevations in ALT $> 5 \times$ ULN; or ALT $> 3 \times$ ULN and total bilirubin $> 2 \times$ ULN, confirmed by immediate repeat testing.
- Creatinine clearance < 30 mL/min

End of Study

The end of the study will be the last participant's last observation (or visit).

1.3. Sample Size and Power

In Part A, a total of approximately 400 participants were randomized in a 1:1 ratio to 2 groups (200 participants per group).

The sample size computation was based on an assumed distribution of the 7-point ordinal scale on Day 14 for Part A Treatment Group 1. The odds ratio represents the odds of improvement in the ordinal scale for Treatment Group 2 relative to Treatment Group 1. The sample size needed to detect a given odds ratio for a 1:1 randomization using a 2-tailed test at level α is given by:

$$12 (z_{\alpha/2} + z_{\beta})^2 / \theta^2 (1 - \sum_{i=1}^7 \rho_i^3)$$

Where θ is the log odds ratio, ρ_i is the overall probability (combined over both treatment groups) of being in the i th category of the ordinal outcome, and $z_{\alpha/2}$ and z_{β} are the $1 - \alpha/2$ and β quantiles of the standard normal distribution {Whitehead 1993}.

A sample size of 400 participants (200 in each group) achieves > 85% power to detect an odds ratio of 1.75 using a two-sided significance level of 0.05. In this sample size calculation, it is assumed that the probability distribution of the ordinal scale at Day 14 for Treatment Group 1 is as follows:

1. Death, 2%
2. Hospitalized, on invasive mechanical ventilation or ECMO, 4%
3. Hospitalized, on non-invasive ventilation or high flow oxygen devices, 7%
4. Hospitalized, requiring low flow supplemental oxygen, 13%
5. Hospitalized, not requiring supplemental oxygen - requiring ongoing medical care (COVID-19 related or otherwise), 16%
6. Hospitalized, not requiring supplemental oxygen - no longer requires ongoing medical care (other than per protocol RDV administration), 20%
7. Not hospitalized, 38%

The sample size calculation was performed using the software PASS (Version 14.0).

The sample size for Part B is based on the anticipated need for RDV and current trends in the COVID-19 epidemic.

2. TYPE OF PLANNED ANALYSIS

2.1. Interim Analyses

2.1.1. Data Monitoring Committee Analysis

The data monitoring committee reviewed the results from the analysis of the Part A Day 14 snapshot.

2.1.2. Primary Analysis

The primary analysis was performed after participants in Part A either completed 14 days or prematurely terminated from Part A on or prior to Day 14.

2.1.3. Part A Final Analysis

The final analysis for participants in Part A was performed after all participants in Part A completed the study or prematurely terminated from the study.

2.2. Final Analysis

The final analysis for this study will be performed after all participants have completed Part B of the study or prematurely terminated from the study, outstanding data queries have been resolved or adjudicated as unresolvable, and the data have been cleaned and finalized. This SAP describes the statistical analysis methods and data presentations to be used for the analysis of Part B.

3. GENERAL CONSIDERATIONS FOR DATA ANALYSES

Analysis results will be presented using descriptive statistics. For categorical variables, the number and percentage of participants in each category will be presented; for continuous variables, the number of participants (n), mean, standard deviation (SD) or standard error (SE), median, first quartile (Q1), third quartile (Q3), minimum, and maximum will be presented.

By-subject listings will be presented for all participants in the All Enrolled Analysis Set unless otherwise specified, and sorted by subject ID number, visit date, and time (if applicable). Data collected on log forms, such as AEs, will be presented in chronological order within a participant. The group to which participants were categorized at baseline per Section 3.2 will be used in the listings.

3.1. Analysis Sets

Analysis sets define the participants to be included in an analysis. Analysis sets and their definitions are provided in this section. Participants included in each analysis set will be determined before database finalization. The analysis set will be included as a subtitle of each table, figure, and listing. A summary of the number and percentage of participants in each analysis set will be provided by group and in total.

3.1.1. All Enrolled Analysis Set

The **All Enrolled Analysis Set** will include all participants who are enrolled into Part B of the study. This is the primary analysis set for by-subject listings.

3.1.2. Expanded RDV Analysis Set

The primary analysis set for efficacy and safety analysis is defined as the **Expanded RDV-Treated Analysis Set**, which will include all participants who (1) are enrolled into Part B of the study and (2) have received at least 1 dose of RDV. Part B participants will be grouped according to their baseline ordinal scale (Mechanically Ventilated or Extension Group).

3.2. Subject Grouping

Part B participants will be grouped according to their baseline ordinal scale (Mechanically Ventilated Group [baseline ordinal scale = 2] or Extension Group [baseline ordinal scale > 2]). This grouping may differ from the categorization at enrollment in the IWRS.

3.3. Strata and Covariates

No formal statistical testing will be performed in the analysis of Part B of the study; therefore, no covariates are planned.

3.4. Examination of Subject Subgroups

3.4.1. Subject Subgroups for Efficacy Analyses

Selected efficacy endpoints will be analyzed for the following subject subgroups:

- Age (years): (a) < 65 and (b) ≥ 65
- Sex at birth: (a) male and (b) female
- Baseline oxygen support status (based on the 7-point ordinal scale): (a) invasive mechanical ventilation, (b) high flow oxygen, (c) low flow oxygen, and (d) room air (See [Appendix 2](#)), where (a) only applies to the Mechanically Ventilated Group and (b) - (d) apply to the Extension Group
- Race: (a) Asian, (b) Black, (c) White and (d) Other. Other includes all races (including Not Permitted) other than Asian, Black, and White
- Region: (a) North America, (b) Europe, and (c) Asia.

3.4.2. Subject Subgroups for Safety Analyses

Incidence of all treatment-emergent AEs (TEAEs) and survival will be summarized for the following subject subgroups:

- Age (years): (a) < 65 and (b) ≥ 65
- Sex at birth: (a) male and (b) female
- Baseline oxygen support status based on the 7-point ordinal scale: (a) invasive mechanical ventilation, (b) high flow oxygen, (c) low flow oxygen, and (d) room air (See [Appendix 2](#)), where (a) only applies to the Mechanically Ventilated Group and (b) - (d) apply to the Extension Group
- Race: (a) Asian, (b) Black, (c) White and (d) Other. Other includes all races (including Not Permitted) other than Asian, Black and White
- Region: (a) North America, (b) Europe, and (c) Asia.

3.5. Multiple Comparisons

Adjustments for multiplicity will not be made, because no formal statistical testing will be performed in the analysis of Part B of the study.

3.6. Missing Data and Outliers

3.6.1. Missing Data

Missing data can have an impact upon the interpretation of the trial data. In general, values for missing data will not be imputed, unless methods for handling missing data are specified.

In this study, a missing pre-treatment laboratory result will be treated as normal (ie, no toxicity grade) for the laboratory abnormality summary. The handling of missing or incomplete dates for AE onset is described in Section 7.2.5.2, and for prior and concomitant medications in Section 7.5.

3.6.2. Outliers

Outliers will be identified during the data management and data analysis process, but no sensitivity analyses will be done to evaluate the impact of outliers on efficacy or safety outcomes, unless specified otherwise. All data will be included in the analyses.

3.7. Data Handling Conventions and Transformations

In general, age collected at Day 1 (in years) will be used for analyses and presented in listings. If age at Day 1 is not available for a participant, then age derived based on date of birth and the first dose date will be used instead. If an enrolled participant was not dosed with any study drug, the enrollment date will be used instead of the Day 1 visit date. For screen failures, the date the first informed consent was signed will be used for the age derivation.

Laboratory data that are continuous in nature but are less than the lower limit of quantitation (LOQ) or above the upper LOQ will be imputed as follows:

- A value that is 1 unit less than the LOQ will be used to calculate descriptive statistics if the datum is reported in the form of “< x” (where x is considered the LOQ). For example, if the values are reported as < 50 and < 5.0, values of 49 and 4.9, respectively, will be used to calculate summary statistics. An exception to this rule is any value reported as < 1 or < 0.1, etc. For values reported as < 1 or < 0.1, a value of 0.9 or 0.09, respectively, will be used to calculate summary statistics.
- A value that is 1 unit above the LOQ will be used to calculate descriptive statistics if the datum is reported in the form of “> x” (where x is considered the LOQ). Values with decimal points will follow the same logic as above.
- The LOQ will be used to calculate descriptive statistics if the datum is reported in the form of “≤ x” or “≥ x” (where x is considered the LOQ).

3.8. Analysis Visit Windows

3.8.1. Definition of Study Day

Study Day 1 is defined as the first dosing date of study drug.

Study Days are calculated relative to Study Day 1 and derived as follows:

- For postdose study days: Assessment Date – First Dosing Date + 1
- For days prior to the first dose: Assessment Date – First Dosing Date

Therefore, **Study Day 1/ First Dose Date** is the day of first dose of study drug administration, as recorded on the Study Drug Administration eCRF form.

Last Dose Date is defined as the maximum, nonmissing, nonzero dose end date of treatment recorded on the Study Drug Administration eCRF form with “Study Drug Permanently Withdrawn” box checked for participants who prematurely discontinued or completed study drug according to the Study Drug Completion eCRF. Refer to [Appendix 2](#) for missing date imputation, if necessary.

Last Study Date is the latest of the study drug start dates and end dates, the clinic visit dates, and the laboratory visit dates, including the 28-day follow-up visit date, and the death date (if applicable, only for participants who prematurely discontinued study according to the Study Completion eCRF).

Baseline value is defined as the last value obtained on or prior to the first dose date (and time, if available) unless otherwise specified (see Section [3.8.3](#)).

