6.5. Day 28 Follow up Assessment (±5 Days)

The following evaluations are to be completed if this visit is conducted in person. For participants who have been discharged from hospital, the final evaluation can be made by phone. Only AE and concomitant medication and ordinal scale (if discharged on or after Day 14) review are to be completed if visit is conducted by phone.

- Physical examination and vital signs (heart rate, temperature, blood pressure)

- Documentation of respiratory status:

Respiratory rate

- Oxygen supplementation: room air, low flow O₂ (L/min and %), high flow O₂ (L/min and %), CPAP/BIPAP (FiO₂ or %), mechanical ventilation (FiO₂ or %), ECMO

Oxygenation: SpO₂ or PaO₂

Radiographic findings (if available)

- Review AEs and document concomitant medications
- Review the Ordinal Scale (Section 6.9). If subject was not discharged by Day 14, any change in category and the date of any change in category from Day 14 to discharge (or Day 28) should be recorded

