6.2. Efficacy Endpoints of Interest

Efficacy endpoints of interest include endpoints based on clinical status assessed by a 7-point ordinal scale. The endpoint will be derived by combining the available death, hospital discharge alive and ordinal scale assessment reported by the site, where death supersedes discharge alive and discharge alive supersedes the ordinal scale score reported by the site.

Sites were instructed to report the worst ordinal scale category for each day. Therefore, the ordinal scale result on the day the participant was discharged alive does not necessarily reflect Not hospitalized (7). The definition of clinical status based on the 7-point ordinal scale is defined as follows:

- If a participant dies while hospitalized (as recorded on the Death eCRF and Hospitalization eCRF), the endpoint on the day of death and all subsequent days through Day 28 will be set to Death (1)
- If the participant is discharged alive, the endpoint on the day of discharge alive and all subsequent days through Day 28 will be set to Not hospitalized (7)
- If the participant is discharged alive and dies on the same day or a later day (as recorded on the Death eCRF and Hospitalization eCRF), the endpoint on the day of discharge alive and all subsequent days until the day of death will be set to Not hospitalized (7). On the day of death and all subsequent days through Day 28, the endpoint will be set to Death (1),

Every effort will be made to obtain clinical status data for all participants prior to discharge alive. The last known clinical status will be used for days with missing clinical status (eg, where the reason for Hospital Discharge is not “Discharged Alive” and the participant has not died). All post-baseline days with missing ordinal scale score, from Day 2 to Day 14 and Day 28, will use the previous last known clinical status.

Efficacy endpoints of interest include

- Clinical status on Days 1 to 14, Day 28 and last available assessment
- Change in clinical status on Days 5, 7, 11, 14, 28, and last available assessment
- Time to clinical improvement (days): Clinical improvement is defined as a ≥ 2 -point improvement from baseline clinical status or discharged alive on the 7-point ordinal scale using the definition specified above.

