6.2.1. Analysis of Efficacy Endpoints of Interest

The number and percentage of participants in each clinical status category for each day from Baseline through Day 14 and at Day 28 and using the last available assessment will be summarized by group. These results will be summarized using (1) the clinical status definition in Section 6.2 and (2) with the definition specified in Section 6.2 but excluding days with missing ordinal scale score not due to death or discharge alive. In addition, stacked bar charts by study day (Baseline through Day 14 and at Day 28) will be produced by group using the definition specified in Section 6.2.

The number and percentage of participants in each clinical status category for each day from Baseline through Day 14 and at Day 28 and last available assessment will be summarized within each subgroup defined in Section 3.4.1.

The change from baseline in clinical status category on Days 5, 7, 11, 14, 28 and last available assessment will be summarized by group using descriptive statistics.

Number of days of oxygen support status modes (invasive mechanical ventilation, high flow oxygen, low flow oxygen) will be calculated as the number of days oxygen support was reported on the 7-point ordinal scale eCRF through death, discharge alive, or Day 14 and presented for each group using descriptive statistics.

A shift table of baseline oxygen support status (death, invasive mechanical ventilation, high flow oxygen, low flow oxygen, room air, discharge alive) to Days 5, 7, 11, 14, 28 and the last available status will be provided for each group.

Duration of hospitalization will be calculated only for participants who are discharged alive on or prior to Day 28 and will be summarized for each group using descriptive statistics.

All-cause mortality will be estimated for each group using the Kaplan-Meier product limit method with all available data. Participants who did not die will be censored at the last study day.

Days to clinical improvement and days to recovery will be estimated for each group using a competing risk analysis approach, with death as the competing risk. Participants without recovery will be censored on the day of the last non-missing ordinal scale assessment.

Forest plots by subgroup will be presented for all-cause mortality Kaplan-Meier estimates on Day 28 and cumulative incidence of recovery on Day 28.

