Hematology	Hemoglobin (g/dL)	1
Hematology	Hematocrit (%)	1
Hematology	Platelet count (x10 ⁹ /L)	0
Hematology	WBC (x10 ⁹ /L)	2
Chemistry	ALT (U/L)	0
Chemistry	AST (U/L)	0
Chemistry	Total bilirubin (mg/dL)	2
Chemistry	Glucose (mg/dL)	0
Chemistry	Serum creatinine (mg/dL)	2
Chemistry	Creatinine Clearance by Cockcroft Gault (mL/min)	1

Standard deviation and standard error will be reported to one more significant decimal place than the raw measurement.

Mean, median, minimum, Q1, Q3, and maximum will be reported to the same number of decimal places of the raw measurements.

Exceptions may be considered; for example, if more than 4 significant digits are provided for the measurement.

- 14) Last dose date is not expected to be missing. However, if last dose date is missing, it will be imputed using the maximum of non-missing, non-zero dose, study drug start and stop dates.
- 15) Incomplete death dates will be imputed as the maximum of the study drug start dates (lasfdt), study drug end dates (lasldt), clinic visit dates (lvis28dt), laboratory visit dates (llab28dt), including the 28-day follow-up visit date plus 1, ie dthdt
 $\max(\text{lasfdt}, \text{lasldt}, \text{lvis28dt}, \text{llab28dt}) + 1$.
- 16) Ordinal scale and oxygen support status

The oxygen support status is derived from the ordinal scale:

Ordinal Scale		Oxygen Support Status
1	Death	Death
2	Hospitalized, on invasive mechanical ventilation or ECMO	Invasive Mechanical Ventilation
3	Hospitalized, on non invasive ventilation or high flow oxygen devices	High Flow Oxygen
4	Hospitalized, requiring low flow supplemental oxygen	Low Flow Oxygen
5	Hospitalized, not requiring supplemental oxygen requiring ongoing medical care (COVID 19 related or otherwise)	Room Air
6	Hospitalized, not requiring supplemental oxygen no longer requires ongoing medical care (other than per protocol RDV administration)	Room Air
7	Not hospitalized	Discharge

17) Censoring rules

Time to death: participants are censored at the last known date alive (last study day)

Time to ≥ 2 -point improvement, time to ≥ 1 -point improvement, time to recovery; if a participant does not experience the event of interest and does not die, the participant is censored at the last non-missing ordinal scale assessment date.

18) Graded Laboratory Abnormalities Summary

The following labels will be used for laboratory abnormalities and Grade 3 or 4 laboratory abnormalities summary tables and listings:

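### The mortality censoring date omits discharge-alive, ordinal-scale and adverse-event dates, so survivors without a Day 28 visit can be censored before a date on which they are documented alive

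*SAP*

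**What the plan says.** **Estimator (SAP 6.2.1).** "All-cause mortality will be estimated for each group using the Kaplan-Meier product limit method with all available data". For survivors, "Participants who did not die will be censored at the last study day". Day 28 is a reporting point: "Forest plots by subgroup will be presented for all-cause mortality Kaplan-Meier estimates on Day 28 and cumulative incidence of recovery on Day 28".

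**Censoring rule (SAP Appendix 2, item 17).** "Time to death: participants are censored at the last known date alive (last study day", so the two terms are treated as one date.

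**Definition (SAP 3.8.1).** "Last Study Date is the latest of the study drug start dates and end dates, the clinic visit dates, and the laboratory visit dates", and the sentence continues: "including the 28-day follow-up visit date, and the death date (if applicable, only for participants who prematurely discontinued study". The hospital discharge date, ordinal-scale record dates and adverse-event dates are not in the list. Item 15 of Appendix 2, which imputes incomplete death dates, draws on the same drug, visit and laboratory dates.

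**What is collected, and when.** Daily assessments run to Day 14 or discharge (Protocol 6.3). After Day 14, ordinal-scale category changes are recorded until discharge or Day 28 (SAP 3.8.2), and adverse events continue to be collected (SAP Appendix 1, footnote b). A Day 28 follow-up is scheduled for everyone, and "For participants who have been discharged from hospital, the final evaluation can be made by phone" (Protocol 6.5).

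**The concern.** A last date known alive should be the latest dated evidence that the participant is alive. The date in SAP 3.8.1 need not be that. Take a survivor with a category change on Day 22, discharge alive on Day 24 and no Day 28 visit. If no clinic visit or laboratory test is dated after Day 14, this person leaves the mortality risk set at about Day 14, although study records show survival to Day 24. Under item 17, the time-to-recovery and time-to-improvement analyses censor at the last ordinal-scale assessment, so they can follow the same person to Day 22 or beyond.

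Early censoring of this kind removes only survivors. Deaths on Days 15-28 are still counted, against a smaller risk set. Part B has no randomized control and no formal testing, so a reader takes the absolute Day 28 estimate at face value, and a bias in one direction does not cancel against a comparator.

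**Working it through.** The documents state no Part B mortality, loss-to-follow-up or censoring figure, so there is no plan figure to reproduce. Two things can be checked: direction and size.

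**Direction.** The Kaplan-Meier estimate is S(28) = product over death days of (1 - d/n), where d is deaths and n is the number at risk. Moving a survivor's censoring date later leaves every d unchanged and can only raise n, so each factor rises or stays the same, and mortality 1 - S(28) falls or stays the same. In 2,000 random data sets, later censoring never raised mortality. The omission therefore biases upward or not at all.

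**Size.** Assumptions, none from the documents:
- true Day 28 mortality 10% or 35%, all deaths in hospital, 65% of them by Day 14 and evenly spread within Days 1-14 and 15-28;
- survivors' discharge days evenly spread over Days 4-28 (25 days);
- 5%, 10% or 20% of survivors with no Day 28 visit, and no other record after Day 14 or discharge;
- other survivors followed to Day 28.

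The SAP rule censors a survivor without a Day 28 visit at the earlier of discharge and Day 14. The comparison censors at discharge.

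*One row in full: 1,000 participants, 35% mortality, 20% missing.*
1. Deaths: 350, of which 0.65 × 350 = 227.5 by Day 14 and 122.5 after.
2. Survivors: 650. Without a Day 28 visit: 0.20 × 650 = 130, or 130/25 = 5.2 per discharge day. Discharged on Days 4-14: 11 × 5.2 = 57.2. Discharged on Days 15-28: 14 × 5.2 = 72.8.
3. The day-by-day product gives S(14) = 0.7670 under both rules, because participants discharged by Day 14 are censored on the same day either way.
4. SAP rule: at risk on Day 15 = 1,000 - 227.5 - 130 = 642.5. With no censoring again before Day 28, the remaining factor is (642.5 - 122.5)/642.5 = 0.8093. S(28) = 0.7670 × 0.8093 = 0.6208, so mortality is 37.92%.
5. Discharge rule: at risk on Day 15 = 1,000 - 227.5 - 57.2 = 715.3, then falling by 8.75 deaths (122.5/14) and 5.2 discharges a day. The remaining factor is 0.8194. S(28) = 0.6285, so mortality is 37.15%.
6. Omitting the discharge date adds 0.77 points. The other 37.15 - 35 = 2.15 points remain.

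*All rows (differences taken before rounding):*

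| True mortality | No Day 28 visit | SAP rule | Censor at discharge | Due to omitted discharge date |
|---|---|---|---|---|
| 10% | 0% | 10.00% | 10.00% | 0 |
| 10% | 5% | 10.22% | 10.17% | 0.05 |
| 10% | 10% | 10.47% | 10.35% | 0.12 |
| 10% | 20% | 11.03% | 10.75% | 0.28 |
| 35% | 0% | 35.00% | 35.00% | 0 |
| 35% | 5% | 35.65% | 35.49% | 0.16 |
| 35% | 10% | 36.35% | 36.01% | 0.33 |
| 35% | 20% | 37.92% | 37.15% | 0.77 |

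The discharge date accounts for about a quarter of the total excess (0.77 of 2.92 points in the last row).

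**If later dated contacts also exist.** Simulated cohorts with mortality of 5-40% and 20% or 50% of discharges after Day 14 show that using a later adverse-event or other contact date as well as discharge lowers the estimate by 0.09-0.52 points with 5% missing, and by 0.42-2.34 points with 20% missing.

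**For scale.** With an assumed 2,000 participants, the 95% half-width is 1.96 × √(0.35 × 0.65/2,000) = 2.1 points at 35%, and 1.3 points at 10%.

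**The case against.** **The Day 28 visit is in the definition.** A reader who stops partway through the sentence in 3.8.1 might infer that survivors in general are dropped at about Day 14 and that Day 28 mortality is overstated. The documents do not support that. The Day 28 visit date is named, the visit is scheduled for all, and survivors who have it are censored there. This objection stands and limits the point to survivors without the visit.

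**Phone contacts probably count.** If they did not, 50-80% of survivors might be censored by Day 14, and a true 20% mortality would then be estimated at about 28-42%. Footnote c of the study procedures table, in both documents, describes the phone contact as a visit conducted by phone, so that reading is not supported. Section 3.8.1 does not mention phone contact, however, and a word there would settle it.

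**The affected case may be rare.** Protocol 6.5 places the recording of category changes after Day 14 within the Day 28 assessment, so a participant with such records will usually have a Day 28 date. The SAP also provides for laboratory values from Day 16 and Day 28 vital signs from Day 15, so some participants will have later qualifying dates. This stands as to frequency. SAP 3.8.2 describes day-by-day recording of changes, so the case remains possible.

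**Most of the excess is loss to follow-up.** This also stands. Censoring at discharge is itself informative, because discharged participants are at lower risk.

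**The ordinal endpoint is not a contradiction.** After discharge alive, SAP 6.2 says "the endpoint on the day of discharge alive and all subsequent days through Day 28 will be set to Not hospitalized (7", unless death is recorded. A reader might infer that the SAP contradicts itself on vital status. It uses two conventions for two outputs, and carrying discharge forward assumes no unrecorded later death, which could bias mortality downward. A second mortality figure built that way is a matter of preference, not a needed correction.

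**Conclusion.** The point holds in limited form. The Last Study Date is not the last known date alive, although item 17 treats them as the same. For a survivor with no Day 28 visit who was discharged after Day 14, or who has an ordinal-scale or adverse-event record after the last visit or laboratory date, the rule censors before a date on which the participant is documented alive.

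The direction is certain: upward or nil. The size is conditional. It is zero when Day 28 follow-up is complete. If 5-20% of survivors lack the visit, leaving out the discharge date adds about 0.05-0.3 points at 10% mortality and 0.15-0.8 points at 35%, and leaving out later contacts adds more where such records exist. The missing-visit rate, mortality levels and timing are assumptions. The discharge-date effects are within the sampling error of a 2,000-participant group. It is therefore a definition to correct, not evidence that the mortality estimate will be materially wrong.

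**What to change.** In SAP 3.8.1 and Appendix 2 item 17, define a separate last-known-alive date as the latest of all dates on which the participant is documented alive: study drug, clinic visit, laboratory, discharge alive, ordinal-scale record, adverse event, and the Day 28 contact, in person or by phone. Censor time to death there, and align the wording of 6.2.1.

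Report by group the number of survivors censored before Day 28, so that readers can judge the loss to follow-up that the definition cannot repair. A footnote should say how many of these had a Day 28 visit early in the ±5-day window, which is a separate and expected cause of censoring before Day 28.

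The cost is one extra derivation and one extra table line. The SAP refers to Hospitalization, Death, ordinal-scale and AE eCRFs, so most of the dates should already be held. The eCRF itself is not among the documents, so the availability of a dated phone contact should be confirmed. If the SAP is already final, the change can be recorded in the clinical study report, as SAP section 1 allows.
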